### **5.7.8 Height and weight**

For height (cm) and weight (kg), the change from baseline to last assessment will be compared between the two treatment groups using an ANCOVA model with baseline value as a covariate and treatment as the main factor. The rate of change in height will be assessed using regression analysis.

Child growth standards for 2007 are available at the WHO website

<https://www.who.int/childgrowth/standards/en/>. This site provides mean and standard deviation for height and weight from 0 to 5 years old by day for males and females. It has mean and standard deviation for height from 5 to 19 years old by month for male and female and for weight from 5 to 10 years old by month for males and females.

Z scores will be calculated by matching sex and age in days until 5 years old and by matching sex and age in months from 5 to 10 years old as follows:

$$\text{(Observed data from LA55} - \text{Mean from WHO data}) / (\text{Standard deviation from WHO data})$$

The change from baseline to last assessment in Z score will be compared between the two treatment groups using an ANCOVA model with baseline value as a covariate and treatment as the main factor.

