### 1.3 Rationale

A recent investigator-led trial that explored whether early-start therapy with deferiprone could delay the progression of iron accumulation without inducing toxicity yielded promising results. Recently diagnosed thalassemia patients aged approximately 12 months were randomized to either start receiving deferiprone at a low dose of 50 mg/kg/day or to wait until their serum ferritin levels reached the threshold of 1000 µg/L recommended by current guidelines. All the subjects who were not receiving chelation reached this threshold at about 6 months post-baseline, after receipt of about 10 transfusions; in comparison, for those on deferiprone, none had reached it by 6 months, only 10% had reached it by 9 months, and the remainder reached it only at 12 months, after 16 to 18 transfusions. Large group differences were seen for other indices of iron overload as well. With respect to safety, there were no unexpected, serious, or severe adverse events associated with deferiprone treatment.

The current trial has been designed to further evaluate the early use of deferiprone in young children with newly diagnosed transfusion-dependent thalassemia. The objectives are to determine whether such a regimen can postpone saturation of transferrin and thus the appearance of labile plasma iron (considered the main source of iron overload in endocrine glands and myocytes) while maintaining a good safety profile. Participants in this trial will have already started on a transfusion regimen designed to maintain a hemoglobin level > 9 g/dL, but will still have a serum ferritin well below 1000 µg/L, which is the current standard for starting iron chelation therapy.

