### 3.2 Rationale for Study Design

The study is placebo-controlled in order to compare the current standard of care of no chelation vs. early-start chelation, on both safety and efficacy measures.

Apart from the use of placebo, the design is similar to that of the earlier investigator-led open-label study, in which the control group received no treatment. The same parameters

that were used in that study to measure iron overload—serum ferritin, transferrin saturation, and labile plasma iron—are used here, with the difference of applying a criterion of 60% rather than 70% for transferrin saturation. The same criterion of discontinuing patients from the study when they reach a serum ferritin level  $\geq 1000 \mu\text{g/L}$  at 2 consecutive visits is maintained, which ensures that patients who are ready to begin standard chelation therapy will not be delayed in doing so.

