#### **9.4.1.4 Analysis of Safety**

Descriptive statistics (mean, standard deviation, minimum, and maximum) will be produced for continuous variables, and frequency tables will be produced for discrete variables by treatment group. Summaries of adverse events and serious adverse events will be produced by treatment group. Shift tables will be generated for comparing the screening/baseline values and end of study values of the relevant measures.

For weight and height, the change from baseline to last assessment will be compared between the two treatment groups using an ANCOVA model with baseline value as a covariate and treatment as the main factor. A similar ANCOVA model will be used for the analysis of the z-scores for height. The rate of change in height will be assessed using regression analysis.

The following safety data will be summarized by treatment group:

- Adverse events (AEs), adverse drug reactions (ADRs), serious adverse events (SAEs), and serious adverse drug reactions (SADRs)
- Number of discontinuations due to AEs
- Hematology assessments
- Biochemistry assessments
- Vital signs
- Urinalysis
- Prior and concomitant medications

Prolactin will be measured at baseline and Month 12. The change in prolactin level from baseline to Month 12 will be compared between the two treatment groups using an ANCOVA model with baseline value as a covariate and treatment as the main factor.

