#### 4.1.1 Serum Ferritin ( $\mu\text{g/L}$ )

Ferritin is a protein that stores iron in a non-toxic form, transports it to areas where it is required, and releases it in a controlled manner, thereby acting as a buffer against iron deficiency and iron overload. It is mainly found in tissues, but small amounts are measured in the serum, where it can serve as an indirect but easily measurable marker of the total amount of iron stored in the body. (Drawbacks of using it as a marker include lack of specificity, as disorders other than iron overload can cause large amounts of ferritin to be released into the circulation, and inter-patient variability.) Levels of serum ferritin above 1000 ng/mL are often considered to be associated with iron toxicity. In young children who have only recently begun an RBC transfusion regimen, it takes some time for this level to be reached, but in the absence of chelation it inevitably is reached.

Serum ferritin is measured at each visit, and the time to reach a level  $\geq 1000 \mu\text{g/L}$  will be compared between the treatment arms. Patient is to be withdrawn from the study when they attain a serum ferritin level  $\geq 1000 \mu\text{g/L}$  at 2 consecutive visits provided that the child has had no signs of infection in the previous 7 days and that CRP level is not greater than 20% higher than the normal range for the patient's age.

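### The raw height and weight comparison to last assessment ignores follow-up time, which is expected to be shorter on placebo; the planned Z-score ANCOVA largely handles this but is not named as the main growth analysis

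*SAP*

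**What the plan says.** **Raw change.** SAP 5.7.8 states that for height (cm) and weight (kg) "the change from baseline to last assessment will be compared between the two treatment groups using an ANCOVA model". The covariate is the baseline value and the factor is treatment; neither follow-up time nor age is in the model. Protocol 9.4.1.4 says the same: "For weight and height, the change from baseline to last assessment will be compared between the two treatment groups using an ANCOVA model".

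**Other growth analyses.** SAP 5.7.8 also defines Z scores matched on sex and age, and adds "The change from baseline to last assessment in Z score will be compared between the two treatment groups using an ANCOVA model". For height velocity it says "The rate of change in height will be assessed using regression analysis", with no model given. The list of tables includes trend tables for height (14.3.3.4) and weight (14.3.4.4). SAP 5.3 words the growth endpoint on the Z-score system. Neither document says which growth analysis is the main one, and SAP section 5 applies the two-sided 0.05 level to every test.

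**Exit rule.** SAP 4.1.1 states "Patient is to be withdrawn from the study when they attain a serum ferritin level" of at least 1000 µg/L at two consecutive visits, subject to the infection and CRP checks. Protocol 5.1 measures weight and height at the early termination visit, which is arranged once the confirming result is known. Protocol 9.2 plans for 70% on deferiprone and 20% on placebo to be below 1000 µg/L at Month 12.

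**Table shells.** Tables 14.3.3.3 and 14.3.4.3 are labelled Month 12, where the text says last assessment. Tables 14.3.3.5 and 14.3.4.5 show Month 12 Z scores with a t-test, where the text says an ANCOVA to last assessment.

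**The concern.** Children gain height and weight simply by being followed for longer. If one arm leaves earlier because of the outcome that the drug is meant to change, raw change to last assessment mixes growth velocity with length of follow-up. Here the expected direction is fixed by the plan: placebo leaves earlier, so the raw test leans towards deferiprone.

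Protocol 1.1 gives growth delay after early treatment with another chelator as a reason why chelation is started late. A growth test that can hide a slowdown, or suggest better growth when velocities are equal, therefore errs in the unwanted direction on a key safety question.

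**Working it through.** **1. The plan's own figure.** Inputs are 32 per arm, 70% v 20%, two-sided 0.05 (protocol 9.2, SAP 5). The pooled proportion is 0.45. The null SE is √(2 × 0.45 × 0.55 / 32) = 0.1244 and the alternative SE is √((0.21 + 0.16) / 32) = 0.1075. Then z = (0.50 − 1.96 × 0.1244) / 0.1075 = 2.38, which gives power of 99.1%. Exact enumeration of Fisher's test gives 98.3%. Both agree with the stated figure of over 90%. The planning rates mean that 30% and 80% are no longer below 1000 at Month 12.

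**2. Follow-up.** A child first at or above 1000 at monthly visit m is confirmed at visit m + 1, so exit is at min(12, m + 1). Mean follow-up = S × 12 + (1 − S) × mean exit, where S is 0.7 or 0.2.

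- Crossings at visits 11–12: all exits at 12, so 12.0 v 12.0 months.
- Visits 10–12: exits 11, 12, 12, mean 11.667. This gives 11.90 v 11.73.
- Visits 7–12: exits 8, 9, 10, 11, 12, 12, mean 10.333. This gives 8.4 + 3.1 = 11.50 v 2.4 + 8.27 = 10.67.
- Constant hazard (an early stress case), summed over visits: 10.52 v 7.15.
- Hybrid of protocol 1.3 timing and protocol 9.2 rates: on placebo 80% cross at 6 and exit at 7, so 0.8 × 7 + 0.2 × 12 = 8.0. On deferiprone 10% cross at 9 and exit at 10 and the other 20% cross at 12, so 0.1 × 10 + 0.9 × 12 = 11.8.

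The hybrid uses the only crossing times in the documents, which come from the earlier study: "All the subjects who were not receiving chelation reached this threshold at about 6 months post-baseline", and on deferiprone "only 10% had reached it by 9 months, and the remainder reached it only at 12 months". Protocol 3.2, in the sentence that starts "The same criterion of discontinuing patients from the study when they reach a serum ferritin level", says that the exit rule is kept from that study.

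**3. Slowdown hidden.** Raw change is about velocity × time. The arms look equal when deferiprone velocity is lower by 1 − (placebo follow-up / deferiprone follow-up). For visits 7–12 this is 1 − 10.67/11.50 = 7.2%; for the hybrid it is 1 − 8.0/11.8 = 32.2%.

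**4. Lag to the termination visit.** The last height is taken after the confirming visit. Adding an assumed lag, capped at Month 12, shortens the gap. For visits 7–12 with one month, exits are 9, 10, 11, 12, 12, 12, mean 11.0, so 11.70 v 11.20 and 1 − 11.20/11.70 = 4.3%. With half a month it is 5.7%. For the hybrid the figure falls from 32% to 29% (half a month) or 26% (one month).

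**5. False findings.** Trials were simulated with 32 per arm and equal velocity in both arms. The assumptions, none of them from the documents, are growth of 0.6 or 1.0 cm/month, between-child velocity SD 25%, measurement error 0.7 cm, baseline height SD 8 cm and reference SD 3.5 cm. The last two columns give the share of trials in which the raw ANCOVA finds deferiprone significantly better (nominal 2.5%).

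| Crossings | Mean follow-up, months (deferiprone v placebo) | Slowdown hidden | No lag | Lag 0.5–1 month |
|---|---|---|---|---|
| Visits 11–12 | 12.0 v 12.0 | 0% | about 2.5% | unchanged |
| Visits 10–12 | 11.9 v 11.7 | 1.4% | about 4% | 2.5–4% |
| Visits 7–12 | 11.5 v 10.7 | 7.2% | 15–18% | 8–12% |
| Constant hazard | 10.5 v 7.1 | 32% | 84–87% | down to about 78% |
| Hybrid | 11.8 v 8.0 | 32% | 99% | somewhat lower |

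The Z-score ANCOVA gives 4–6% false positives (two-sided) in every pattern.

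**6. A true 15% slowdown on deferiprone, no lag.** The raw test detects it in 53–61% of trials (visits 11–12), 17–20% (visits 7–12) and 0% (both early patterns). In the hybrid it calls deferiprone better in 66–73% despite the slowdown. The Z-score ANCOVA detects it in 54–75% across the patterns. A lag softens the raw-test figures. All simulated figures are good to a few points. Only height was simulated; weight follows the same logic.

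**The case against.** The case for leaving the plan alone is substantial. The Z-score ANCOVA is already planned, and SAP 5.3 words the endpoint on Z scores. Trend tables are listed for height and weight. SAP 5.6 already contains a rate-per-month model with a treatment-by-month term and a slope difference; it names only ferritin, LPI and TSAT, but the growth trend tables share its layout. Unequal follow-up would be visible in the time-to-withdrawal curves (SAP 5.7.7), the exposure tables (14.4.4 and 14.4.5) and the numbers per visit. The raw, trend and Z-score tables would all appear, so none replaces another. The SAP ranks no safety analysis at all, and the shells are expressly open to change.

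The timing is also uncertain. The earlier study's children were about 12 months old, whereas this trial admits children up to 10 years and expects 20% of placebo to stay below 1000, so crossings may come later. The hybrid pattern stands in neither section on its own. Exits for other reasons, such as neutropenia on deferiprone, are not modelled.

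All of this stands, and it limits the harm. It does not remove the point. The raw ANCOVA is a stated comparison, reported with a confidence interval, whose expected bias has a known direction. It can disagree with the Z-score ANCOVA, and nothing in the SAP says which then governs.

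**Conclusion.** The point holds as a matter of ranking and labelling. The raw cm and kg ANCOVA is expected to lean towards deferiprone under the plan's own rates. The lean is negligible if crossings come after about Month 10. It is modest if they spread over visits 7–12 (about 8–18% false findings, the lower end with a lag to the termination visit). It is large if they are early (about 78–99%). These figures rest on assumed crossing times, growth rates and SDs.

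A reader might infer three stronger things that the documents do not support:

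- That the growth evaluation as a whole is unsound. It is not: the planned Z-score ANCOVA removes most of the bias.
- That a false finding in 78–99% of trials is the expected result. Those figures need early crossings, and protocol 9.2 together with the wide age range allows later ones.
- That the height regression has no basis in the SAP. SAP 5.6 supplies a usable template, though only by analogy.

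Severity is minor to moderate. The primary endpoint, sample size and data collection are not affected.

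**What to change.** In SAP 5.7.8:

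- Name the planned ANCOVA of Z-score change, baseline to last assessment, as the main growth analysis for height and for weight.
- Report raw cm and kg change descriptively, or with follow-up time in the model.
- As support, apply the treatment-by-month slope model of SAP 5.6 to height and weight, preferably with child-level slopes, and give the slope difference with its 95% CI.
- Align Tables 14.3.3.3, 14.3.3.5, 14.3.4.3 and 14.3.4.5 with the text: last assessment and ANCOVA. Read literally, the Month 12 labels would drop early leavers; in the hybrid pattern about 6 of 32 placebo children would remain (0.2 × 32 = 6.4).

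**Cost.** A few sentences and four table labels, with no new data and no new main model.

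**Downsides.** Z scores depend on the reference standard. If both arms grow 10% slower than the reference, the Z-score ANCOVA falsely shows deferiprone as worse in 3–9% of simulated trials (nominal 2.5%), because that arm is followed longer. Z scores also do not equalise exposure time for an effect that builds up. Child-level slopes avoid the reference problem but are noisier for early leavers: they detect a 15% slowdown in 33–47% of trials under constant hazard, against 53–64% otherwise. The weight reference described in SAP 5.7.8 stops at 10 years, so a child who passes that age on study needs a stated rule.

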### 4.2 Inclusion Criteria

Individuals will be eligible to enroll in the study if they meet **all** the following criteria:

1. Male or female aged  $\geq 6$  months to  $< 10$  years
2. Confirmed diagnosis of beta-thalassemia, as determined by high performance liquid chromatography (HPLC) or DNA testing
3. Started on a regular RBC transfusion regimen, with a minimum of 2 transfusions already completed
4. Screening levels of serum ferritin greater than  $>200 \mu\text{g/L}$  but not more than  $600 \mu\text{g/L}$ .  
Since SF level may be impacted by the presence of infection, it must additionally be verified that the child has had no signs of infection in the previous 7 days, including the day of screening, and that the level of C-reactive protein (CRP) is no greater than 20% higher than the normal range for the patient's age. If there are signs of infection and/or the CRP level is above this threshold, the SF level must be checked again a minimum of

one week later. (Note: If an investigator has valid reason to believe that an out-of-range SF level may be attributable to infection even if this is not indicated by the CRP result, SF may be rechecked once more a minimum of one week later.)

5. Parent(s) or legal guardian (as per local requirements) must provide signed and dated written informed consent prior to the first study intervention, and must verify that patient will be able to adhere to study restrictions, appointments, and evaluation schedules. If applicable, patients who are old enough will additionally provide assent.

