### **5.3 Safety Endpoints**

The safety endpoints are:

- Adverse events (AEs): Frequency, intensity, time to onset, duration, and relatedness to study drug
- Serious adverse events (SAEs): Frequency, intensity, time to onset, duration, and relatedness to study drug
- Number of discontinuations due to AEs
- Growth parameters: Weight, height, and height velocity, as classified using the Z-score system
- Change in prolactin level from baseline to Month 12

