estimate 'Deferiprone - Placebo at Month 10'
  treat 1 -1
  treat*month  0 0 0 0 0 0 0 0 0  1 0 0
                0 0 0 0 0 0 0 0 0 -1 0 0/ cl alpha=0.05;
estimate 'Deferiprone - Placebo at Month 11'
  treat 1 -1
  treat*month  0 0 0 0 0 0 0 0 0  1 0
                0 0 0 0 0 0 0 0 0 0 -1 0/ cl alpha=0.05;
estimate 'Deferiprone - Placebo at Month 12'
  treat 1 -1
  treat*month  0 0 0 0 0 0 0 0 0  1
                0 0 0 0 0 0 0 0 0 0 -1/ cl alpha=0.05;
run;

```

A Kaplan-Meier survival curve for the time to reach a serum ferritin level  $\geq 1000 \mu\text{g/L}$ , an LPI value  $\geq 0.6 \mu\text{M}$ , or a TSAT value  $\geq 60\%$  will be generated for the two treatment groups. Log-rank test will be used for comparing the two survival curves for each of the 3 efficacy endpoints.

As an example, for serum ferritin, the following SAS code of LIFETEST procedure will be used to compare the two survival curves. A variable status is the censoring indicator. A status of 1 indicates an event time when a serum ferritin level reaches  $\geq 1000 \mu\text{g/L}$  and a status of 0 indicates the event of serum ferritin level  $\geq 1000 \mu\text{g/L}$  has not occurred by the end of the study.

```

proc lifetest data=sf method=km plot=(s) graphics;
  time month*status(0);
  strata treat;
run;

```

Trend analysis over time for LPI, TSAT, and SF measures will be performed to compare the rate of change per month in these measures between the two treatment groups. As an example, for serum ferritin, the following SAS code of MIXED procedure will be used to compare the two slopes between the two treatment groups:

```
proc mixed data=sf;
  class treat patient;
  model sf = treat month treat*month / noint solution;
  repeated / type=ar(1) Patient=patient(treat);
  estimate 'Slope for deferiprone' month 1 treat*month 1 0;
  estimate 'Slope for placebo' month 1 treat*month 0 1;
  estimate 'Slope for deferiprone minus placebo' treat*month 1 -1;
run;
```

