### **14.3.3 Height**

Table 14.3.3.1 Height (cm) at each assessment

Table 14.3.3.2 Change in height (cm) from baseline to at each follow-up assessment

Table 14.3.3.3 LS Means for change in height (cm) from ANCOVA model at Month 12

Table 14.3.3.4 Trend analysis for height (cm) over time

Table 14.3.3.5 Z score analysis for height (cm)

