Data source: 16.2.9.5 Listing of vital signs

Table 14.3.3.5 Z score analysis for height (cm)

	Deferiprone		Placebo		
	N	Mean ± SD (Min, Max)	N	Mean ± SD (Min, Max)	P-value (t-test)
Baseline	xx	x.x ± x.x (x.x, x.x)	xx	x.x ± x.x (x.x, x.x)	0.xxxx
Month 12	xx	x.x ± x.x (x.x, x.x)	xx	x.x ± x.x (x.x, x.x)	0.xxxx
Change	xx	x.x ± x.x (x.x, x.x)	xx	x.x ± x.x (x.x, x.x)	0.xxxx

Data source: 16.2.9.5 Listing of vital signs

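### Height velocity is listed as a Z-score endpoint but analysed only as a slope in cm per month, a scale that leans modestly towards an apparent deficit on deferiprone because placebo children are expected to leave earlier

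*SAP*

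**What the plan says.** SAP 5.3 lists among the safety endpoints "Growth parameters: Weight, height, and height velocity, as classified using the Z-score system", and Protocol 9.1.3 uses the same wording.

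For velocity, SAP 5.7.8 says only "The rate of change in height will be assessed using regression analysis". The matching output is "Table 14.3.3.4 Trend analysis for height (cm) over time". Its shell has a single row, the monthly rate of change by arm, with the difference and a p-value. No model, covariate or age band is given for height. The nearest slope model that the SAP writes out is the serum ferritin one in SAP 5.6, "model sf = treat month treat*month / noint solution", with an AR(1) covariance.

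Z-scores are defined in SAP 5.7.8 for attained height and weight only. Of the WHO reference it says "This site provides mean and standard deviation for height and weight from 0 to 5 years old by day for males and females", and from age 5 it describes monthly values; no velocity reference is named. For these Z-scores, "The change from baseline to last assessment in Z score will be compared between the two treatment groups using an ANCOVA model". Protocol 9.4.1.4 plans the same kind of model for height Z.

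Two design features matter. Entry runs from 6 months to under 10 years (Protocol 4.2), with no age stratification stated (Protocol 5.2). A child leaves at Month 12 or when SF is at or above 1000 µg/L at two consecutive visits (Protocol 3.1).

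**The concern.** The velocity endpoint is not produced on the scale on which it is listed. That follows from the documents without any assumption.

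The scale also matters in this design. A child's height curve bends downwards with age, steeply in infancy. A straight line fitted to six months of it is steeper than one fitted to twelve. The sample size section expects 70% on deferiprone and 20% on placebo still below the ferritin threshold at Month 12, so placebo lines will usually be the shorter ones. The cm slope can then favour placebo when the drug does nothing to growth.

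Protocol 1.1 gives growth delay after early deferoxamine as a reason for the present caution about early chelation, so a growth result from this trial will be read closely in either direction.

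**Working it through.** **Inputs from the documents.** 32 per arm; 70% v 20% with SF below 1000 at Month 12; two-sided 0.05 (Protocol 9.2, SAP 5). The documents give no effect size or power for growth. The one related figure, power above 90% for the primary endpoint, reproduces: 99.1% by the normal approximation and 98.3% by exact enumeration with Fisher's test.

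**Assumed, because the documents do not give them.** Exponential exit times; growth curves (steep: 17 falling to 5.5 cm/year; mild: 12 falling to 6 cm/year); entry ages uniform over 0.5–2, 0.5–5 or 0.5–10 years. The 70% and 20% are treated as the proportions still in follow-up at Month 12.

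**Step 1: follow-up.** Hazard h = −ln(s)/12 and mean follow-up = (1 − s)/h.
- Deferiprone: h = −ln(0.7)/12 = 0.0297, so 0.3/0.0297 = 10.1 months.
- Placebo: h = −ln(0.2)/12 = 0.1341, so 0.8/0.1341 = 6.0 months.
- Gap: 4.1 months. Protocol 1.3 reports that unchelated children in the earlier trial reached the threshold at about 6 months.

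**Step 2: closed form.** If velocity falls by c cm/month per month, a line fitted over T months has slope v₀ − cT/2. The difference in mean slope with no drug effect is −(c/2) × 4.1. For c = 0.01, 0.02 and 0.033 this gives −0.021, −0.041 and −0.068 cm/month. The last value holds only if every child slows that fast.

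**Step 3: simulation with no drug effect.** 1,200 runs per scenario. Slope differences are deferiprone minus placebo. "False deficit" in the table means a significant result against deferiprone (nominal 2.5%; simulation error about ±0.9 points).

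| Curve, entry age (years) | AR(1) model, cm/month | False deficit | Per-patient slopes, cm/month | False deficit | Per-patient Z slopes, Z/month | False deficit |
|---|---|---|---|---|---|---|
| Steep, 0.5–2 | −0.025 | 3.0% | −0.041 | 12.9% | −0.0006 | 3.3% |
| Steep, 0.5–5 | −0.014 | 2.3% | −0.022 | 6.3% | 0.0000 | 2.7% |
| Steep, 0.5–10 | −0.007 | 2.4% | −0.013 | 3.8% | −0.0006 | 2.5% |
| Mild, 0.5–2 | −0.012 | 0.3% | −0.019 | 7.4% | −0.0001 | 3.0% |
| Mild, 0.5–5 | −0.008 | 0.6% | −0.011 | 3.6% | −0.0003 | 2.1% |
| Mild, 0.5–10 | −0.005 | 1.4% | −0.007 | 3.9% | −0.0002 | 3.1% |

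Over a year the cm figures run from 0.005 × 12 = 0.06 to 0.041 × 12 = 0.5 cm.

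Other readings of regression analysis behave differently (600 runs each). A pooled within-patient slope gave −0.001 to −0.011 cm/month. A regression with no patient term was so variable (SD 0.14 to 0.56 cm/month) that no bias could be detected.

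**Step 4: age range.** With equal follow-up in both arms (120 runs) age mixing gave no systematic difference. Chance imbalance does move the estimate. Under the steep curve, a deferiprone arm older by one SD of the chance difference shifts it by correlation × SD of the slope difference: 0.66 × 0.039 = 0.026 cm/month at ages 0.5–2 (SD of age difference 0.11 years), and 0.62 × 0.049 = 0.030 at ages 0.5–10 (SD 0.70 years). Either arm can be the older one.

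**Step 5: the neighbouring analyses.** In the same simulations the ANCOVA of change in height Z to last assessment was off by only −0.005 to +0.001 Z. The ANCOVA of raw change in cm to last assessment favoured deferiprone by 2.1 to 3.0 cm, because 4.1 extra months even at 6 cm/year is 4.1 × 0.5 = 2.1 cm of growth.

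**The case against.** The strongest reply is that growth already has an age- and sex-standardised comparison. The ANCOVA of change in Z in SAP 5.7.8 is essentially unbiased here, and any odd cm slope would be read beside it. That stands, and it limits the point to velocity. It does not supply the velocity endpoint. The shell for Table 14.3.3.5 also shows baseline, Month 12 and change with a t-test, not change to last assessment by ANCOVA. Taken literally, it would rest on about 0.2 × 32 ≈ 6 placebo children. The SAP says that shells may change, so this needs only alignment.

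The second reply is that if height uses the AR(1) form of SAP 5.6, false deficits stay at 0.3% to 3.0%, hardly above nominal. That also stands. The higher rates need a per-patient slope test that the SAP does not name. But the SAP does not name the AR(1) form for height either, and under it the point estimate still leans against deferiprone.

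The third is that a slope of height-for-age Z is not a Z-score from a velocity reference. This is correct, and the result should be labelled accordingly. No velocity reference is named in the plan.

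A reader might infer that mixing ages 6 months to under 10 years itself creates a false deficit. Under 1:1 randomisation it does not: it widens the interval and allows chance imbalance in either direction.

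**Conclusion.** The mismatch between the listed endpoint and its analysis is certain. The bias that follows is real in direction but modest: about 0.005 to 0.04 cm/month against deferiprone with no drug effect, roughly 0.1 to 0.5 cm/year. It is largest if most children are under 2 years. It needs both earlier placebo exit and slowing growth, and its size rests on the assumed growth curves, entry ages and exit times. Whether false-positive risk rises depends on the regression chosen.

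Two stronger readings are not supported. One applies infant deceleration to every child: a fall from 1.4 to 0.85 cm/month over 18 months is 0.0306 per month, and an assumed 3.5-month follow-up gap gives 0.0306 × 3.5/2 = 0.054 cm/month, about 0.6 cm/year. That exceeds all six simulated scenarios and conflicts with an entry range reaching almost 10 years. The other is that the plan can only produce a false signal of harm. The raw-cm ANCOVA errs the opposite way and could hide a deficit, while the change-in-Z ANCOVA is sound. The change should be made, but the trial's growth assessment does not fail without it.

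**What to change.** - In SAP 5.7.8, fit the Table 14.3.3.4 slope model to height-for-age Z-score at each visit, using the formula already there, and write the model out.
- Preferably include a random patient intercept and slope. In the simulations the AR(1) model fitted to Z was unbiased but over-cautious (false deficits 0.0% to 0.1% against 2.5%), while per-patient Z slopes held 2.1% to 3.3%. The random-slope model itself was not simulated.
- Report the between-arm difference in Z per year with a 95% CI as the height velocity result. Describe it as change in height-for-age Z per year, not as a velocity-reference Z-score.
- Label the cm slope descriptive and read it beside the change-in-Z ANCOVA. Add a note that raw-cm change to last assessment depends on length of follow-up.
- Align the Table 14.3.3.5 shell with the last-assessment ANCOVA in the text.

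The cost is a short SAP paragraph, one model statement and two edited shells. Monthly heights are already scheduled, so no new data are needed.

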### **14.3.4 Weight**

Table 14.3.4.1 Weight (kg) at each assessment

Table 14.3.4.2 Change in weight (kg) from baseline to at each follow-up assessment

Table 14.3.4.3 LS Means for change in weight (kg) from ANCOVA model at Month 12

Table 14.3.4.4 Trend analysis for weight (kg) over time

Table 14.3.4.5 Z score analysis for weight (kg)

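### Weight Z-scores use a linear mean/SD formula with no allowance for skewness, so if the weight reference is right-skewed the size of any weight-Z effect in light children is understated

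*SAP*

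**What the plan says.** Weight is a listed safety endpoint. SAP 5.3 reads "Growth parameters: Weight, height, and height velocity, as classified using the Z-score system", and Protocol 9.1.3 has the same item.

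SAP 5.7.8 gives the derivation. Of the WHO website it says: "This site provides mean and standard deviation for height and weight from 0 to 5 years old by day for males and females". "Z scores will be calculated by matching sex and age in days until 5 years old", and by sex and age in months from 5 to 10 years. The formula is the observed value minus the "Mean from WHO data", divided by the "Standard deviation from WHO data". It is one formula for both measures. The SAP gives no skewness term, no check of distributional shape and no separate rule for weight.

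The scores are then analysed as follows: "The change from baseline to last assessment in Z score will be compared between the two treatment groups using an ANCOVA model". Table 14.3.4.5 reports the weight Z-scores.

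Protocol 9.4.1.4 plans a Z-score ANCOVA for height only: "A similar ANCOVA model will be used for the analysis of the z-scores for height". The weight-Z ANCOVA is therefore an SAP addition. SAP 5.7.8 also plans an ANCOVA of weight change in kg.

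**The concern.** A mean and an SD describe a reference fully only when it is symmetric and close to normal. If the reference is right-skewed, its lower tail is short and its upper tail is long, and a single SD is too wide a yardstick below the mean. A light child then scores nearer to 0 than the child's centile implies, and each further kilogram lost moves the score too little. Above the mean the error reverses.

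Growth matters in this trial. Protocol 1.1 cites growth delay in children with mild iron overload who started deferoxamine very young, and this trial tests an early start. Ages run from 6 months to under 10 years, and of the growth analyses in SAP 5.7.8 only the Z-scores allow for age and sex. With 64 children, the growth conclusion will lean on estimates and intervals as much as on p-values, and the estimate is the part that skewness would distort.

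**Working it through.** The documents state no figure for the weight Z-score, so there is nothing of the plan's own to reproduce.

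**Inputs from the documents.** The linear formula and the ANCOVA on change in Z (SAP 5.7.8); 32 children per arm (SAP 3.2); two-sided 0.05 (SAP 5).

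**Assumed inputs.** Neither document gives the shape of the weight reference. Take weight at a fixed age and sex, scaled to median 1, as Box-Cox normal with power L from 0.8 (mild right skew) to −0.6 (strong right skew) and coefficient of variation S from 0.10 to 0.15.

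**Formulas.**
- Skewness-adjusted score: Z = [(x/M)^L − 1]/(L × S). With M = 1, a child at true Z weighs x = (1 + L × S × Z)^(1/L).
- SAP score: (x − mean)/SD, with the mean and SD of that same distribution.
- At L = 1 the two are identical.

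**Mild end, L = 0.8, S = 0.10** (mean 1.0010, SD 0.0999).
- True −2: x = 0.84^1.25 = 0.8042. The SAP score is (0.8042 − 1.0010)/0.0999 = −1.97.
- True −2.5: x = 0.80^1.25 = 0.7566. The recorded fall is (0.8042 − 0.7566)/0.0999 = 0.476.

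**Strong end, L = −0.6, S = 0.15** (mean 1.0187, SD 0.1588).
- True −2: x = 1.18^(−1/0.6) = 0.7589. The SAP score is (0.7589 − 1.0187)/0.1588 = −1.64.
- True −2.5: x = 1.225^(−1/0.6) = 0.7130. The recorded fall is (0.7589 − 0.7130)/0.1588 = 0.289.

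| L | S | true −2 reads | true fall of 0.50 reads | understated by |
|---|---|---|---|---|
| 1 | any | −2.00 | 0.50 | 0% |
| 0.8 | 0.10 | −1.97 | 0.48 | 5% |
| 0.5 | 0.10 | −1.92 | 0.44 | 11% |
| 0.2 | 0.10 | −1.88 | 0.41 | 17% |
| −0.3 | 0.12 | −1.77 | 0.35 | 30% |
| −0.6 | 0.15 | −1.64 | 0.29 | 42% |

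On the heavy side, a true +2 reads 2.03 at the mild end and 2.35 at the strong end.

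**Between-arm effect.** The planned ANCOVA was run on very large simulated samples. Further assumptions: baseline Z has SD 1, individual change has SD 0.4, and the true arm difference is −0.30.
- Mean true Z of 0: the estimate is −0.299 (L = 0.8, S = 0.10) to −0.286 (L = −0.6, S = 0.15). That is a shrinkage of about 0% to 5%, because compression in light children is largely offset by expansion in heavy ones.
- Mean true Z of −1.5: the estimate is −0.290 to −0.203 at the same two ends. That is a shrinkage of about 4% to a third.

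**Test behaviour.** With 32 per arm, mean true Z −1.5, log-normal weight (L = 0) and S from 0.12 to 0.18, 3,000 simulated trials per setting gave a type I error of 4.6% to 5.0% with the SAP formula. Power was 82% to 83%, against 83% to 84% with the skewness-adjusted score.

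**The case against.** The strongest reply is that the premise is not in the documents. Neither one describes the shape of the weight distribution or mentions L, M and S; SAP 5.7.8 says only that a mean and SD are available. Without skew nothing is wrong. This stands, and it is why the size is given as a range that starts at nil.

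Four stronger readings are tempting, and the documents do not support them.
- A reader might infer that the SAP score is invalid unless weight is normal. (x − mean)/SD is a legitimate standardisation for any distribution; normality is needed only to read it as a centile or against a normal-theory cut-off.
- A reader might take the 5% to 42% in the table as the bias in the treatment comparison. It describes one child falling from −2.0 to −2.5. The contrast between arms shrinks far less unless the trial population is light on average, and the eligibility criteria (Protocol 4.2 and 4.3) do not select on weight.
- A reader might infer that the plan is tilted towards finding no growth harm. Both arms get the same formula, and error rates hardly change. Weight in kg, weight trend and the height analyses are also planned, and the formula for weight Z does not touch them.
- A reader might infer that children will be misclassified in a planned table. The shell of Table 14.3.4.5 shows mean, SD, range and a t-test, with no count below a threshold.

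What is left is that a listed safety endpoint uses a formula that can only match or fall short of the skewness-adjusted one, at a stage when changing it is easy.

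**Conclusion.** The point holds as a minor, conditional one. If the weight reference is right-skewed, the planned weight Z-scores are too close to 0 for children well below the mean and under-record their further decline. Over the assumed range, a true −2 reads −1.97 to −1.64 and a true 0.50 fall reads about 0.48 to 0.29.

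At trial level the damage is to the size of the weight-Z effect, by about 0–5% with a mean Z near 0 and about 4% to a third with a mean Z near −1.5, and to the reading of a Z value as a centile. The validity and power of the test are nearly unchanged.

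The result rests on assumed L, S and mean Z, none of which the documents give. With L = 1 there is no error at all.

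**What to change.** In SAP 5.7.8, derive weight-for-age Z as [(x/M)^L − 1]/(L × S), using the reference's L, M and S for the child's sex and age where it supplies them. Keep the linear formula wherever the reference has L = 1; confirm from the reference whether that is so for height. If no skewness parameters are available for some ages, say so and justify mean/SD there.

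Use these values in the Z-score ANCOVA and in Table 14.3.4.5. In the same edit, align the table's shell with the text: the shell shows t-tests at baseline, at Month 12 and on change, while SAP 5.7.8 specifies ANCOVA of change to the last assessment.

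The cost is one formula in the SAP and in the derivation program. No new trial data are needed, and the result is identical if the reference has no skew.
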